9.3 Enrolment visit

- Informed consent and eligibility will be checked by the research team (PIs, research nurse or practitioner).
- Demographics and medical history will be collected.
- Participants will be randomly allocated to one of the 4 study groups in a 1:1:1:1 ratio.
- Randomisation will be performed by an electronic randomisation system.
- Participants will provide a 15ml venous blood sample for biochemical and immunological analysis. A subgroup of participants will be invited to have a maximum 60ml blood sample taken for further immunological analysis. Venous blood samples will be collected by a phlebotomy trained Research Nurse/Practitioner using a vacutainer system or syringe and butterfly.
- Participants randomised to the positive mood intervention will receive a 15 minute positive mood intervention consisting of a combination of positive mood stimuli previously shown to enhance mood in older adults. Participants will also receive information on how to access their positive mood intervention over the next 6 days. Daily reminders to complete the intervention and e-diary will be sent via secure SMS messaging and checked by the PI and/or Research Nurse. In the event a participant is unable to work the e-diary, alternatives can be provided, such as paper copies or phone calls.
- Participants randomised to standard over the counter vitamin D supplement, will be advised to buy and take this immediately prior to vaccination and once daily for the following 27 days. Reminders will be sent to complete the intervention and e-diary as for the positive mood intervention group.
- Participants will then receive their COVID-19 booster and influenza vaccination in the standard NHS clinic which will be running at the site on that day. The vaccine will not be given as part of the study and the type of vaccine, timing or method will not be impacted by their participation in the study.

Some participants, clinicians' and other stakeholders' will then be interviewed about the intervention and trial acceptability and determine the barriers and facilitators to implementing the intervention in routine care. Interviews will be conducted by telephone, video call or face-to-face at participant preference, audio-recorded (with permission) and transcribed verbatim.

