10.1 Adverse event definitions

Adverse Event (AE)	Any untoward medical occurrence in a participant to whom a medicinal product has been administered, including occurrences which are not necessarily caused by or related to that product.
Adverse Reaction (AR)	An untoward and unintended response in a participant to an investigational medicinal product which is related to any dose administered to that participant. The phrase "response to an investigational medicinal product" means that a causal relationship between a trial medication and an AE is at least a reasonable possibility, i.e., the relationship cannot be ruled out. All cases judged by either the reporting medically qualified professional or the Sponsor as having a reasonable suspected causal relationship to the trial medication qualify as adverse reactions.

**University of
Nottingham**
Health Service

Serious Adverse Event (SAE)
	
A serious adverse event is any untoward medical occurrence that:
 
 • results in death • is life-threatening • requires inpatient hospitalisation or prolongation of existing hospitalisation • results in persistent or significant disability/incapacity • consists of a congenital anomaly or birth defect*. 
Other 'important medical events' may also be considered a serious adverse event when, based upon appropriate medical judgement, the event may jeopardise the participant and may require medical or surgical intervention to prevent one of the outcomes listed above.
 
NOTE: The term "life-threatening" in the definition of "serious" refers to an event in which the participant was at risk of death at the time of the event; it does not refer to an event which hypothetically might have caused death if it were more severe.
 
NOTE: Pregnancy is not, in itself an SAE, but an adverse outcome of pregnancy, for example spontaneous miscarriage, may be judged to be an SAE if clinically appropriate.

Serious Adverse Reaction (SAR)
	
An adverse event that is both serious and, in the opinion of the reporting Investigator, believed with reasonable probability to be due to one of the trial treatments, based on the information provided.

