10.2 Assessment of causality

**University of
Nottingham**
Health Service

Causality will be clinically assessed relative to the interventions administered during the trial by the Chief Investigator. An adverse event is considered to have a causal relationship to an intervention if the attribution is possible, probable, or very likely by the definitions listed below. An adverse event is considered to have no causal relationship to an intervention if the attribution is not related or unlikely by the definitions listed below. In the group receiving two interventions, the attribution of any adverse event to either of the individual interventions will be at the Chief Investigator’s discretion.

Causality term	Assessment criteria
0 No relationship	No temporal relationship to study product and Alternate aetiology (clinical state, environmental or other interventions); and Does not follow known pattern of response to study product
1 Unlikely	Unlikely temporal relationship to study product and Alternate aetiology likely (clinical state, environmental or other interventions) and Does not follow known typical or plausible pattern of response to study product.
2 Possible	Reasonable temporal relationship to study product; or Event not readily produced by clinical state, environmental or other interventions; or Similar pattern of response to that seen with other vaccines
3 Probable	Reasonable temporal relationship to study product; and Event not readily produced by clinical state, environment, or other interventions or Known pattern of response seen with other vaccines
4 Definite	Reasonable temporal relationship to study product; and Event not readily produced by clinical state, environment, or other interventions; and Known pattern of response seen with other vaccines

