10.4 Safety reporting procedures

SAEs and AESIs will be reported to the CI as soon as possible after being reported to a member of the team. The CI will be responsible for deciding whether the participant is able to continue the study; whether the study can continue; and whether the sponsor should be informed.

Assignments of causality will only be made in relation to the administration of Vitamin D and/or positive mood intervention during the study. Any SAEs which occur following externally administered vaccines or medicines e.g., those given as part of the patient's usual care, will be judged to be unrelated to the study vaccine and should additionally be reported through national pharmacovigilance mechanisms as applicable.

Hospitalisation (including inpatient or outpatient hospitalisation for an elective procedure) for a pre-existing (existing prior to administration of Vitamin D during the study) condition that has not worsened unexpectedly does not constitute an SAE. Emergency department attendances should not routinely be reported as SAEs unless they meet the SAE definition described above.

The procedure for reporting of Serious Adverse Events is to complete an SAE report form for all reportable SAEs. The CI or delegate will submit (in addition to the expedited reporting above) DSURs once a year throughout the clinical trial, or on request, to the Competent Authority (MHRA), Ethics Committee, HRA (where required), Host NHS Trust and Sponsor. The safety profile will be continuously assessed by the Investigators. The CI and relevant investigators (according to the study delegation record) will also review safety and SAE issues as they arise.

**University of
Nottingham**
Health Service

11. Statistics

Evaluation of the findings will be conducted by the study team using SPSS and overseen by the study statistician [name].

The main statistical analysis will be to identify a statistically significant difference in the four groups and identify any additional immune effect of vitamin D supplementation given at the time of vaccination. We will use a range of advanced techniques, such as multivariate statistical methods and advanced clustering and classification approaches to assess the independent and combined contribution of psycho-behavioural factors to immunological responses to the vaccination.

All validated measures employed will be summarised according to published guidelines.

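### Sections 10.2 and 10.4 use vaccine-trial causality wording in a trial with no study vaccine, so usual-care vaccine reactions grade as Probable for vitamin D or mood and the SAE rule has no clear meaning

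*Protocol*

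**What the plan says.** Section 9.3 puts vaccination outside the trial: "The vaccine will not be given as part of the study". Section 10.4 limits attribution accordingly: "Assignments of causality will only be made in relation to the administration of Vitamin D and/or positive mood intervention during the study". The next sentence in Section 10.4 then says that "Any SAEs which occur following externally administered vaccines or medicines" "will be judged to be unrelated to the study vaccine", and adds national pharmacovigilance reporting.

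Section 10.2 has causality assessed relative to the trial interventions. Grades 0 and 1 refer to the pattern of the study product, but grade 2 (Possible) includes "Similar pattern of response to that seen with other vaccines", and grades 3 (Probable) and 4 (Definite) also use a vaccine pattern. The text above the table counts possible, probable or *very likely* as causal; the table has no such top grade, only Definite.

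Two further provisions of Section 10.4 belong here. Hospitalisation for a pre-existing condition that has not worsened unexpectedly is not an SAE, with pre-existing defined as "existing prior to administration of Vitamin D during the study". The Chief Investigator also decides "whether the sponsor should be informed", whereas the adverse-reaction definition in Section 10.1 covers "All cases judged by either the reporting medically qualified professional or the Sponsor as having a reasonable suspected causal relationship".

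**The concern.** These rules decide which events are called related to vitamin D or mood, and which hospitalisations count as SAEs. They appear to have been written for a trial whose product is a vaccine. Here the vaccine is background care that everyone is due to receive on the day the interventions start, so it is the most obvious competing explanation for early events. A grading scheme that treats resemblance to a vaccine reaction as evidence for the study intervention points the wrong way. Related events can be counted only in the three arms with an intervention, so this over-attribution cannot be balanced in usual care. Separately, staff faced with an SAE cannot tell from Section 10.4 whether they still have a causality judgement to make.

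**Working it through.** No sample size, error rate or event count bears on this point and the plan gives no figure to reproduce. The check is of the table's and/or logic and of the passages against each other.

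**Inputs.** Interventions under assessment: vitamin D and mood (10.4). Vaccination: visit 1, all arms (9.2), not part of the study (9.3). Vitamin D starts immediately before vaccination (9.3). Safety window: consent to day 168 (10). Cut for a causal relationship: Possible or above (10.2). Allocation 1:1:1:1 (7), at least 10 per arm, or 20 if recruitment resumes (11.1).

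**Grades as written.** Let T = reasonable temporal relationship, E = not readily produced by clinical state, environment or other interventions, V = pattern seen with other vaccines.

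- Possible = T or E or V
- Probable = T and E or V. The bracketing is not given, so both are tried: (a) (T and E) or V; (b) T and (E or V)
- Definite = T and E and V

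| Event | T | E | V | Possible | Probable (a) | Probable (b) | Definite |
|---|---|---|---|---|---|---|---|
| 1. Ordinary vaccine reaction soon after visit 1 | yes | no | yes | yes | yes | yes | no |
| 2. Event specific to vitamin D or mood | yes | yes | no | yes | yes | yes | no |
| 3. Vaccine-like event, no temporal link, other cause present | no | no | yes | yes | yes | no | no |

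Events 1 and 2 receive the same grade, so the table does not separate a reaction to the usual-care vaccine from an effect of the intervention. Event 3 is at least Possible, yet if it does not fit the pattern of the study product it also meets every criterion of grade 0.

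E = no for event 1 assumes that the usual-care vaccine counts among the other interventions, which the table does not say. If it did not count, E would be yes and event 1 would be Definite.

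**After replacing V** by S = known pattern of the study intervention, with the vaccine named as an alternative cause:

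- Event 1 (T yes, E no, S no): Possible yes; Probable no under (a) and (b).
- Event 2 (T yes, E yes, S yes, if the pattern is a known one): Definite yes.
- Event 3 (T no, E no, S no): not Possible.

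Event 1 falls from Probable to Possible and remains on the causal side of the cut, because T alone is enough.

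**The study-vaccine sentence.** Literal reading: no study vaccine exists, so nothing is decided about vitamin D or mood. Alternative reading, with study intervention in place of study vaccine: vaccination is at visit 1 and reporting runs to day 168, so practically every SAE after visit 1 follows an external vaccine and would be unrelated whatever Section 10.2 gives.

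**The exemption.** Two of four arms (usual care, mood alone) receive no vitamin D: 2 × 10 = 20 of about 40 participants, or 2 × 20 = 40 of about 80.

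**Sponsor.** Section 10.1 lets a judgement by either the reporting professional or the sponsor make an event an adverse reaction. Section 10.4 leaves to the Chief Investigator whether the sponsor learns of an SAE. The sponsor cannot judge a case that it has not received.

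**The case against.** The strongest objection is that the study-vaccine sentence is leftover text. A reader might infer that Section 10.4 declares all SAEs after vaccination unrelated to vitamin D and mood. The documents do not support that as the plain meaning: the sentence names the study vaccine, the sentence before it keeps causality assessment for the two interventions, and the national reporting is described as additional. This stands. The blanket exclusion is one of two readings, and the defect is that the text does not settle which applies.

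A reader might also infer that genuine vitamin D or mood events would be called unrelated. They would not: the *or* in Possible keeps them on the causal side, and only the top label is lost. This too stands. It is also true that new comparator wording alone does not take vaccine reactions below the causal cut.

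On the exemption, vitamin D starts at visit 1, so dating pre-existing conditions from visit 1 in all arms is a natural guess. That makes a difference in SAE counting between arms unproven, but the text still supplies no reference point for two arms. On the sponsor, either party's judgement suffices, SAE forms are completed for reportable events, yearly safety reports go to the sponsor, and Section 12 gives it direct access. So the sponsor is not wholly cut off, but none of these guarantees that an individual SAE reaches it promptly.

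**Conclusion.** The concern holds as a fault of wording with practical consequences. As written, a typical reaction to the usual-care vaccine grades as Probable for the study intervention under either bracketing; a vaccine-like pattern alone gives at least Possible without any temporal link; and Definite is out of reach for an event specific to vitamin D or mood. The study-vaccine sentence is either empty or in conflict with Section 10.2. The top causal term has no matching grade, the exemption lacks a reference point in two of four arms, and the notification rule does not fit the sponsor's role in Section 10.1.

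The grading result assumes that the table's connectives are applied as printed and that the usual-care vaccine counts as an alternative cause. It would be tempting to conclude that the trial's safety results cannot be interpreted. That goes too far: the synopsis lists feasibility and acceptability as primary and immune response as exploratory, safety is not a listed objective, and about 40 participants are planned. The point should be fixed, but it does not undermine the primary objective.

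**What to change.** Reconcile Sections 10.1, 10.2 and 10.4 with Section 9.3:

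- In grades 2 to 4, replace the vaccine comparator with the study intervention (vitamin D or mood), and name the usual-care vaccine among the alternative causes. This lowers typical vaccine reactions to Possible and closes the route to Possible by vaccine pattern alone. It does not make events with only a temporal link unrelated. State the bracketing of Probable.
- Delete or reword the study-vaccine sentence so that each SAE is assessed individually against vitamin D and/or mood.
- Use one term for the top grade in both text and table.
- Give the pre-existing-condition exemption one reference point that exists in all four arms.
- Reconcile the Chief Investigator's discretion over informing the sponsor with the sponsor's causality role in Section 10.1, so that SAEs reach the sponsor.

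The cost is an amendment to the protocol and SAE form wording, and a few more SAE notifications.

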
Suspected Unexpected Serious Adverse Reaction (SUSAR)
	
A serious adverse reaction, the nature and severity of which is not consistent with the Reference Safety Information for the medicinal product in question set out:
 
 • in the case of a product with a marketing authorisation, in the approved summary of product characteristics (SmPC) for that product • in the case of any other investigational medicinal product, in the approved investigator's brochure (IB) relating to the trial in question.

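### Section 10.4 exempts unplanned admissions for a foreseeable worsening of a pre-existing condition from SAE status, contradicting the unqualified hospitalisation criterion in section 10.1

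*Protocol*

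**What the plan says.** Section 10.1 defines a serious adverse event by its outcome. One criterion is that the event "requires inpatient hospitalisation or prolongation of existing hospitalisation". Nothing there refers to pre-existing disease or to whether the event was foreseeable. Death, threat to life and lasting disability are separate criteria, and there is a judgement-based route: "Other 'important medical events' may also be considered a serious adverse event when, based upon appropriate medical judgement". Expectedness appears in the definitions only at the SUSAR step: "A serious adverse reaction, the nature and severity of which is not consistent with the Reference Safety Information for the medicinal product in question".

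Section 10.4 adds an exemption. It begins "Hospitalisation (including inpatient or outpatient hospitalisation for an elective procedure) for a pre-existing (existing prior to administration of Vitamin D during the study" and ends by saying that such a "condition that has not worsened unexpectedly does not constitute an SAE". The next sentence deals with emergency department visits: "Emergency department attendances should not routinely be reported as SAEs unless they meet the SAE definition described above".

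Section 10.2 words its causality rule for adverse events in general: "An adverse event is considered to have a causal relationship to an intervention if the attribution is possible, probable, or very likely".

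**The concern.** The two sections classify the same event differently, and the protocol does not say which prevails. Four consequences hang on SAE status:

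- prompt reporting to the Chief Investigator, who then decides whether the participant and the study continue and whether the sponsor is told (10.4);
- completion of an SAE form (10.4);
- mandatory follow-up of events unresolved at the end of the study or on discontinuation (opening of section 10);
- eligibility to be classed as a serious adverse reaction or a SUSAR, both of which must first be serious (10.1).

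An admission ruled exempt under 10.4 loses all four. The ruling turns on the word *unexpectedly*. The protocol gives no criterion for it and does not say who judges it.

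**Working it through.** The protocol gives no figure on this point, so the check is a reading of the two sections against each other.

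**Step 1: is the exemption confined to planned care?** No. The elective procedure stands in an *including* parenthesis, which names an example and sets no limit. The emergency department sentence does not narrow it, because it concerns attendances and not admissions.

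**Step 2: which courses of disease does the exemption cover?** The condition is that the disease has not worsened unexpectedly. There are three cases for an admission due to a pre-existing condition:

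| Course of the condition | Hospitalisation criterion in 10.1 | Exemption in 10.4 |
|---|---|---|
| (a) Not worsened, e.g. a planned procedure | Arguably not reached, since nothing untoward has happened | Exempt |
| (b) Worsened, as could be foreseen | Serious | Exempt |
| (c) Worsened unexpectedly | Serious | Not exempt |

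The sections conflict in case (b).

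**Step 3: how much of case (b) escapes?** Section 10.4 exempts the hospitalisation only. If the event is also fatal, life-threatening, disabling or judged an important medical event, 10.1 still makes it an SAE. The gap is the part of case (b) that is serious through hospitalisation alone.

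**Step 4: what remains for those events?** Section 9 says adverse events are recorded, 10.2 covers their causality, and section 10 provides for participant notification and for review of primary care records at days 28 and 168. Prompt reporting to the Chief Investigator is required only for SAEs and adverse events of special interest, and 10.1 does not define the latter. If the participant does not report an admission that occurs just after day 28, the next planned look at the records is up to 168 − 28 = 140 days away.

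**Step 5: possible size, on assumptions.** Follow-up is 40 × 168/365.25 = 18.4 person-years, or 80 × 168/365.25 = 36.8 if recruitment resumes. The protocol gives no admission rate. The two ranges used here are assumptions: 0.15 to 0.30 unplanned admissions per person-year, with 50% to 80% of them for a pre-existing condition.

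- 40 participants: 18.4 × 0.15 = 2.8 to 18.4 × 0.30 = 5.5 admissions; 2.8 × 0.5 = 1.4 to 5.5 × 0.8 = 4.4 for a pre-existing condition.
- 80 participants: 36.8 × 0.15 = 5.5 to 36.8 × 0.30 = 11.0 admissions; 5.5 × 0.5 = 2.8 to 11.0 × 0.8 = 8.8 for a pre-existing condition.

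These are ceilings on the number affected. They include case (c) and events that meet another seriousness criterion, all of which stay SAEs. The true number could be zero.

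**The case against.** Several stronger readings are tempting, and the text does not support them.

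- *Such an admission can never be an SAE.* The other criteria in 10.1 still apply, so this is wrong.
- *Relatedness is never asked.* Section 10.2 covers any adverse event. What is lost is handling as a serious event, not all causality assessment.
- *The order of seriousness, causality and expectedness is reversed.* In 10.4 *unexpectedly* describes the course of the participant's own disease. In the SUSAR definition, expectedness is judged against a product's Reference Safety Information. That step is untouched.
- *The comparison of SAE counts between arms is distorted.* The protocol plans no such comparison. Its primary objective is feasibility and acceptability, and its exploratory outcomes are immunological.
- *Most SAEs in the trial would be lost.* That would only restate the assumed share of admissions. The synopsis title refers to healthy adults and section 8.3 excludes people too frail to take part, so the assumed rates may be too high.

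A further defence is that a worsening brought on by an intervention departs from the expected course of the disease and so falls outside the exemption. This is a fair reading, and it may make the affected group small. But it requires a view on causality before the exemption is applied, and 10.4 does not ask for one. Where the worsening looks like the ordinary course of the disease, the wording lets the admission leave the serious-event pathway without that question being put at that level.

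These points limit the consequence. They do not remove the conflict between 10.1 and 10.4.

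**Conclusion.** The point holds in a narrow form. An unplanned admission for a foreseeable worsening of a pre-existing condition, serious only through hospitalisation, is an SAE under 10.1 and not an SAE under 10.4. If 10.4 is followed, the event bypasses prompt SAE reporting, the SAE form, SAE follow-up and the serious-reaction categories, while remaining recordable and assessable as an adverse event.

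This conclusion rests on the wording alone. The number of events cannot be derived from the protocol. On the assumed rates the ceiling is 1.4 to 4.4 admissions in 40 participants, or 2.8 to 8.8 in 80, with zero possible. The consequence is modest for a feasibility trial, but the contradiction should be removed because the protocol itself states both rules.

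**What to change.** Reconcile 10.1 and 10.4 by rewriting one sentence in 10.4. Limit the exemption to elective or pre-planned admissions for a pre-existing condition that has not worsened, and delete *unexpectedly*. For example: *An elective or pre-planned admission for a pre-existing condition that has not worsened is not an SAE; all other admissions are classified under section 10.1.* Causality, and then expectedness where it applies, are judged after that classification. The reference date that defines *pre-existing* need not change for this purpose.

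The cost is one sentence in an amendment and a few more SAE forms for admissions that prove unrelated.
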